Primer Aligner Study NCT02550938 July 7, 2015

Study Summary

| Title | Primary Aligner Study |
|-----------------------------------|--|
| Objectives | The primary objective was to determine the impact of primer aligners in both the 7 aligner set Invisalign treatment and the 12 aligner set Invisalign treatment. Results were measured by total treatment time (in days), and refinement rate per cohort. |
| Purpose | The purpose of this study was to demonstrate that allowing time for the biological response of the periodontal ligament (PDL) resulted in successful achievement of clinical outcomes and subject/doctor satisfaction. |
| Relevant Scientific Background | Align offers treatment options to treat minor tooth movements. These products consist of a limited number of aligners in a treatment. One of the clinical barriers to adoption for treatments requiring a pre-set low number of aligners can be the lack of clinical outcomes and predictability in the set number of aligner sets. A potential explanation for this hypothesis is that a biological delay, or "lag", in tooth movement occurs at the beginning of treatment. This lag is usually quantifiable and takes up to 3 aligner sets for the biological response to begin. This biological delay may particularly impact low number aligner treatments. |
| Design | This was a non-significant risk, multicenter, randomized prospective study. A total of twenty-one (21) doctors participated in this study, 13 in the U.S. and eight (8) in the U.K. There were 253 subjects enrolled into the study, 198 from the U.S. and 55 from the U.K. All subjects received Invisalign® Full treatment per the standard Invisalign® Instructions for Use. Subjects were randomly placed into one of four different cohorts: Cohort 1: 7 aligner Cohort wear time 1 Cohort 2: 7 aligner cohort wear time 2 Cohort 4: 12 aligner cohort wear time 1 |
| Primary Outcomes | Total treatment time (in days) and refinement rate (%) was compared between the 7 aligner and 12 aligner cohorts. Subjects were followed for the duration of orthodontic treatment, an average of 37 weeks/262 days. |
| Treatment | The Invisalign [®] System. |

| Eligibility Criteria | Inclusion Criteria: |
|----------------------|--|
| | A subject were considered eligible if all of following inclusion criteria were fulfilled: |
| | Subject must have fully erupted dentition Age range ≥18 years old (Adult subject) |
| | • Subjects who are indicated for either: 5, 7, 10, or 12 aligner sets |
| | Exclusion Criteria: |
| | A subject was considered ineligible if any one of the following exclusion criteria were fulfilled: |
| | Subject who has unerupted, erupting, partially erupted dentition (except for 2nd and 3rd molars) |
| | Subject who has mixed dentition |
| | Subject with periodontal disease |
| | Subject with active caries |
| | Subject with TMD symptoms |
| | Subject has undergone pre-treatment with any orthodontic appliance 3 months prior to the start of treatment |
| | Subject has undergone any accelerated orthodontic treatment prior to or during treatment as part of this study |
| | Subject has known allergy to latex or plastic |
| | Subjects who are pregnant or will become pregnant during treatment |
| Sites | 21 participating doctors in the US and UK. |
| Sample Size | 215 subjects. |
| Length of Study | Approximately 4 years. |
| Results | Subject Enrollment |
| | • Started: 253 |
| | 178 female |
| | o 75 male |
| | Completed: 215 |
| | Not completed: 38 |
| | 215 completed subjects were included in the data analysis which was |
| | conducted by Align's own statisticians. These 215 subjects all had initial and |
| | final data points for analysis. Total treatment time was measured in days and |
| | mai uata points for analysis. Total tredthent time was measured in uays and |

| refinement rate was measured as a percentage per cohort. No Adverse Events |
|--|
| were reported. |
| |

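### The stated primary comparison, 7 against 12 aligners, does not estimate the primer effect within either aligner count that the objective asks for

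*Protocol*

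**What the plan says.** Everything relevant is in the protocol's Study Summary table.

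- **Objectives** sets the aim as to "determine the impact of primer aligners in both the 7 aligner set Invisalign treatment and the 12 aligner set Invisalign treatment". That is two effects, one within each aligner count. The row adds: "Results were measured by total treatment time (in days), and refinement rate per cohort".
- **Design** says: "Subjects were randomly placed into one of four different cohorts". Only Cohorts 1, 2 and 4 can be read in the text available, and none is labelled as primer or comparator. The gap may come from text extraction, and nothing below relies on it.
- **Primary Outcomes** names the only comparison in the document: "Total treatment time (in days) and refinement rate (%) was compared between the 7 aligner and 12 aligner cohorts".
- **Results** reports that "215 completed subjects were included in the data analysis" and that "refinement rate was measured as a percentage per cohort". It names no contrast.

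**The concern.** The objective asks what primers do when the number of aligners is held fixed. The stated comparison varies the number of aligners and says nothing about primers. Treatment time shows the difficulty most plainly: a 12-aligner course can differ in length from a 7-aligner course because of the count alone, whatever primers do.

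Followed as written, the primary result is a difference by aligner count. It can be near zero when primers work in both counts, and large when they do nothing. The stated objective would then have no primary comparison behind it, although the 215 analysed subjects may well allow one.

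**Working it through.** The protocol gives no effect size, SD, refinement rate, allocation ratio or cohort size. There is therefore no planned figure to reproduce; only the count 253 − 38 = 215 can be checked, and it agrees. Every other input below is an assumption.

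**1. What the 7-versus-12 contrast estimates.** For count k (7 or 12), let m_k be the mean outcome without primers, d_k the primer effect and s_k the share of subjects given primers. The mean for that count is m_k + s_k·d_k, so

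12 minus 7 = (m12 − m7) + (s12·d12 − s7·d7).

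This is one number with two unknown primer effects and an unknown count effect. Neither d7 nor d12 can be recovered from it.

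**2. Size of the primer term for refinement rate** (percentage points; d = −20 means a 20-point reduction).

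| d7 | d12 | s7 | s12 | s12·d12 − s7·d7 |
|---|---|---|---|---|
| −20 | −20 | 1/2 | 1/2 | −10 + 10 = 0 |
| −20 | −20 | 1/2 | 1/3 | −6.7 + 10 = +3.3 |
| −20 | −20 | 1/3 | 1/2 | −10 + 6.7 = −3.3 |
| −20 | −20 | 2/3 | 1/3 | −6.7 + 13.3 = +6.7 |
| −20 | 0 | 1/3 | any | +6.7 |
| −20 | 0 | 1/2 | any | +10 |
| −20 | 0 | 2/3 | any | +13.3 |

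The same benefit in both counts can add nothing, or a few points in either direction. None of these values can be told apart from an aligner-count difference of the same size.

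**3. The same point in days.** Take equal shares and average treatment times of 200 days (7 set) and 320 days (12 set). Within-count effects (7 set, 12 set) of (0, 0), (30, 30), (−30, −30) and (30, −30) days all give 7 minus 12 = 200 − 320 = −120 days. With equal weights the contrast over the four cohort means is (½, ½, −½, −½). It is orthogonal to both within-count contrasts: ½·1 + ½·(−1) = 0 for (1, −1, 0, 0), and likewise for (0, 0, 1, −1).

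**4. Chance of a significant result for refinement rate.** The test is a pooled two-sided z-test at 5%, with rejection probabilities from exact enumeration of the binomial distributions. Each cohort has 54 subjects (215/4 = 53.75), with one primer and one comparator cohort in each count.

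| Scenario | Rates | 7 v 12 | Each within-count test |
|---|---|---|---|
| Primers work in both counts, no count effect | 40% → 20% | 4.5% | 63% |
| | 30% → 10% | 4.4% | 76% |
| | 50% → 30% | 4.4% | 57% |
| Primers do nothing, the counts differ (7 set / 12 set) | 40% / 20% | 90% | 5% |
| | 30% / 10% | 97% | 5% |
| | 50% / 30% | 85% | 4–5% |

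No such figures are offered for treatment time, because the protocol gives no SD.

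**5. Precision of the contrast the objective needs.** The 95% half-width for a difference of two proportions is 1.96·√(2p(1 − p)/n), with the 215 subjects split equally.

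| Rate p | 7 v 12 (n = 107.5 per side) | Within one count (n = 53.75 per side) |
|---|---|---|
| 10% | 8.0 points | 11.3 points |
| 30% | 12.3 points | 17.3 points |
| 50% | 13.4 points | 18.9 points |

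The ratio is √2 ≈ 1.41 throughout.

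**The case against.** The best defence is that the sentence is loosely worded. It speaks of cohorts in the plural, the design has four, and refinement rate is reported per cohort. The authors may have meant a comparison among all cohorts. If each count contains a primer and a comparator cohort, a reader could subtract two reported rates to obtain the within-count effect. The SAP, which was not available for this review, may also name the right contrast.

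This leaves open what analysis was actually done, but it does not rescue the text. The literal words name the aligner-count contrast, and reporting a rate per cohort is not a comparison. The complaint is also not that SAP detail is missing: the protocol itself names a primary comparison that does not match its own objective. If the SAP names another, the two documents conflict.

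Three further points stand in part.

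- The numbers above illustrate the problem under assumed inputs and do not measure harm in this trial.
- The legible text does not show that each count has a comparator cohort, so the fix has to be conditional.
- The Relevant Scientific Background row says "This biological delay may particularly impact low number aligner treatments", so differences by count are of legitimate interest. That supports keeping 7 versus 12 as a description. It does not make it an estimate of the primer effect.

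**Conclusion.** The concern holds, with high confidence, and must be fixed. The Primary Outcomes row fixes a contrast that does not answer the Objectives row, whatever the missing cohort label says and whatever the shares of subjects given primers. That conclusion rests on the two rows and the identity in step 1, not on any assumed figure.

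Its practical size does depend on assumptions. Under those in step 4, a 20-point primer benefit in both counts is detected by the stated comparison no more often than chance (about 4–5%, against 57–76% for a within-count test). A 20-point count difference with no primer effect is declared significant 85–97% of the time. The defect lies in the stated comparison and not necessarily in the randomisation.

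**What to change.** Reword the Primary Outcomes row so that total treatment time and refinement rate are each compared between the primer cohort and its comparator cohort, within the 7-aligner group and separately within the 12-aligner group. Name the cohorts in each comparison. Keep 7 versus 12 as descriptive. In addition:

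- If the compared cohorts differ in scheduled days per aligner, report the observed difference in treatment time beside the scheduled difference.
- If a count has no comparator cohort, say that the primer effect in that count cannot be estimated, and narrow the objective and conclusion to match.
- The document describes a finished study. If the within-count contrast was not pre-specified elsewhere, such as in the SAP, disclose that it was restated after data collection. The row should claim the new comparison only once the re-analysis has been done.

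**Cost.** Where comparators exist, this means rewording one row and re-analysing existing randomised data, with no new subjects or procedures. Intervals become about 1.4 times wider under an equal split. There are four primary comparisons (two outcomes by two counts) instead of two, so their multiplicity should be addressed. A contrast chosen after data collection carries less weight. Where no comparator exists, re-analysis cannot repair the gap, and the cost is a narrower claim.

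### Does the accelerated-treatment exclusion remove randomised subjects from the comparison for something that happens after randomisation?

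*Protocol*

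**What the plan says.** The protocol is a single Study Summary table. Its Eligibility Criteria row introduces the exclusions with "A subject was considered ineligible if" any one of them is met, and gives no other consequence. One of the lines reads "Subject has undergone any accelerated orthodontic treatment prior to or during treatment as part of this study". The line before it is anchored to entry: "Subject has undergone pre-treatment with any orthodontic appliance 3 months prior to the start of treatment". The last line of the list, on pregnancy, covers current pregnancy and also pregnancy arising while treatment is in progress.

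The Design row says "Subjects were randomly placed into one of four different cohorts", where a cohort is defined by the number of aligners and the wear time. The Primary Outcomes row says "Total treatment time (in days) and refinement rate (%) was compared between the 7 aligner and 12 aligner cohorts".

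The Results row gives 253 started, 215 completed and "Not completed: 38". It then says "215 completed subjects were included in the data analysis which was" carried out by the sponsor's own statisticians, and adds "These 215 subjects all had initial and" final measurements. It gives no reasons for non-completion. The document contains no separate rule on co-treatment, withdrawal or protocol deviations.

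**The concern.** An eligibility criterion should be decidable before allocation. Half of this one is not: whether a subject has tooth movement accelerated during study treatment is known only after the cohort has been assigned. Taken with the lead-in, the line makes a properly randomised subject ineligible in retrospect.

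If such subjects were then taken out, the groups compared would no longer be the groups randomised. The trigger may also be related to the outcome, since a treatment meant to speed up tooth movement could plausibly shorten total treatment time. The document does not state that link; it is inferred from the name of the treatment. If the use of acceleration differed between cohorts, for instance because subjects on one schedule were more impatient, removing those subjects could bias the comparison. The contrast with the preceding line, which is tied to the period before treatment starts, shows that the authors could have drawn the distinction here and did not.

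**Working it through.** No formula for error rate or sample size applies. The question is what the text does to the analysed set, and that can be checked from the counts and by reading the rows together.

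**Counts (Design and Results rows)**

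- Started: 198 U.S. + 55 U.K. = 253, and 178 female + 75 male = 253. These agree.
- Completed: 253 − 38 = 215, which matches the stated 215.
- Completers left out of the analysis: 215 completed − 215 analysed = 0.
- Share not completing: 38/253 = 15.0%. Share analysed: 215/253 = 85.0%.

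**What the counts settle.** There is no step between completing and being analysed at which a subject was lost. A subject who was accelerated during the study and still completed with data is therefore among the 215. The document does not describe ineligibility as a filter on the analysed set, and the numbers leave no room for one among completers.

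**What the counts leave open.** A subject could have been taken off study under this line and counted among the 38. Zero and 38 are the logical limits, but that range is simply the whole group of non-completers. The same limits would hold for any other conceivable reason for leaving, so they say nothing about this line in particular and are not a measure of its effect.

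**Reading the rows side by side**

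| Place | What it fixes |
|---|---|
| Exclusion lead-in | Meeting a criterion means ineligible; nothing on withdrawal or removal from analysis |
| Accelerated-treatment line | Entry condition and on-study condition joined in one sentence |
| Pregnancy line | Same construction: a current state and a later event joined |
| Results row | Analysis by completion and by data at both ends of treatment |

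Two of the criteria put an on-study restriction in the exclusion list. That points to a drafting habit rather than a deliberate rule for removing subjects after allocation. The lead-in does give one literal consequence, so the label itself is not ambiguous. What is unstated is narrower: whether a randomised subject who becomes ineligible stays on treatment, leaves, or is analysed as assigned.

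**What a change would achieve.** Three edits suggest themselves.

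1. *Split the line into an entry condition and an on-study condition.* The document is in the past tense and reports enrolment and completion, so the edit cannot affect who entered or how they were managed.
2. *Analyse accelerated subjects in their assigned cohort, with a sensitivity analysis excluding them.* Those with outcome data are already in the 215. Those without final data cannot be recovered by rewording an eligibility line. Sensitivity analyses and the handling of deviations are commonly set out in a SAP, which is not at hand.
3. *Count how many of the 38 left for this reason, by cohort.* This is a reporting item. It corrects nothing that the plan states.

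**The case for a change.** The strongest argument for acting is that eligibility belongs in the protocol and this criterion is written there, so an unseen SAP cannot excuse it. Read as it stands, it makes a randomised subject ineligible for a later event. The reasons for 38 withdrawals are not given, so nobody can show that the line did no harm. The pregnancy criterion having the same flaw widens the problem rather than excusing it, and separating the two kinds of condition would be cheap.

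Much of this stands. The line is badly built, the literal reading is the right literal reading, and a count of zero among the 38 would close the matter. What does not follow is that the plan's analysis is at fault. The criterion produces a post-randomisation exclusion only if someone acts on it by withdrawing or dropping a subject, and the document neither instructs this nor shows it. The possibility that some of the 38 left under this line cannot be excluded, but nothing in the text supports it over any other reason for leaving. Whatever their reasons, those subjects are absent because the analysis is confined to completers. That is a separate and larger question, and redrafting this line would not touch it.

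**Conclusion.** No change to the plan is called for. The accelerated-treatment line mixes an entry condition with an on-study one and does not say what follows for a randomised subject. It is an editorial slip, shared with the pregnancy line, and a sensible analyst would treat the second half as a restriction during the study. Its shown effect on the analysed set is nil: 0 of 215 completers were left out. The number of non-completers who left because of it is unknown, and no bias in either direction can be stated.

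This rests on three assumptions: that the Results row describes the analysed set in full; that completing meant finishing treatment with data and not also staying eligible; and that allocation came before study treatment, which follows from the cohorts being defined by aligner number and wear time. If records showed that subjects were withdrawn under this line, and unequally across cohorts, the point would need to be looked at again.

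### The analysis set is the 215 completers: 38 of 253 starters (15.0%) are dropped on an event that follows allocation and also ends total treatment time, which can bias the cohort comparison.

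*Protocol*

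**What the plan says.** The only document at hand is the Protocol's Study Summary.

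- **Design row.** "There were 253 subjects enrolled into the study, 198 from the U.S. and 55 from the U.K", and "Subjects were randomly placed into one of four different cohorts".
- **Primary Outcomes row.** "Total treatment time (in days) and refinement rate (%) was compared between the 7 aligner and 12 aligner cohorts". Also, "Subjects were followed for the duration of orthodontic treatment", with an average given as 37 weeks or 262 days.
- **Results row.** 253 subjects started and 215 completed; "Not completed: 38". The analysis set follows: "215 completed subjects were included in the data analysis". It adds "These 215 subjects all had initial and" final data points. On the second primary outcome it says "refinement rate was measured as a percentage per cohort".

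The document names no other analysis set. It does not say how the 38 were handled, why they left, or which cohorts they came from.

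**The concern.** Membership of the analysis set is decided by something that happens during treatment. The cohorts differ in number of aligners and in wear time, so both the chance of leaving and the kind of subject who leaves could differ between them. The document does not report whether they did.

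The two primary outcomes are exposed in different ways:

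- **Total treatment time.** The event that admits a subject to the analysis is also the event that ends the measured time. If subjects with long or difficult courses tend to leave, completer means are too short, and more so in the cohort that loses more of them.
- **Refinement rate.** The denominator becomes each cohort's completers. A refinement ordered for a subject who later left would not be counted. The document does not say whether there were any.

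At stake is whether an observed cohort difference can be read as an effect of the assigned treatment. An analysis of finishers also cannot show whether failure to finish differed by cohort.

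**Working it through.** **1. The Protocol's own counts (Design and Results rows).**

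- Completed plus not completed: 215 + 38 = 253, equal to the number started.
- By country: 198 + 55 = 253. By sex: 178 + 75 = 253.
- Share left out: 38/253 = 0.1502, or 15.0%. Share analysed: 215/253 = 0.8498.

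The subject flow reproduces exactly. Cohort sizes, the cohort split of the 38, refinement rates and standard deviations are not given, so what follows uses stated assumptions.

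**2. What drives the between-cohort bias.** In cohort j, let d_j be the share missing and D_j the difference between the missing and the completers in mean outcome. Then

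all-starters value = completer value + d_j × D_j,

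and moving from completers to all starters shifts the cohort difference by d_1 × D_1 − d_2 × D_2. This is zero if d and D both match across cohorts. Otherwise it is generally not zero, and the document does not allow it to be computed.

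**3. Logical bounds for the refinement rate, taken as yes/no for every subject.** With n_j subjects in group j, m_j of them missing, the lower bound for a group counts none of its missing as refined and the upper bound counts all of them. The difference between two groups then lies in a band of width

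m_1/n_1 + m_2/n_2, with m_1 + m_2 = 38.

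For the pooled 7- and 12-aligner groups:

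| Assumed group sizes | Width of band |
|---|---|
| 126.5 and 126.5 | 38/126.5 = 30.0 points, however the 38 split |
| 101.2 and 151.8 (40:60) | 38/151.8 = 25.0 to 38/101.2 = 37.5 points, depending on the split |

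The split moves the band. With equal groups and equal completer rates, a 19/19 split gives −15.0 to +15.0 points. With a 10/28 split and an assumed completer rate of 10% in both groups:

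- upper: [(116.5 × 0.10 + 10) − 98.5 × 0.10]/126.5 = 11.8/126.5 = +9.3 points
- lower: [116.5 × 0.10 − (98.5 × 0.10 + 28)]/126.5 = −26.2/126.5 = −20.7 points

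**4. Wear-time contrast within one aligner number.** Assume four equal cohorts of 253/4 = 63.25, each losing 38/4 = 9.5. The band for two of them is (9.5 + 9.5)/63.25 = 30.0 points, so the exposure is no smaller there.

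**5. Treatment time, by illustration.** Assume that true treatment time has the same gamma distribution in both groups, with mean 262 days (borrowed from the stated average), and that the longest courses are the ones lost. Completer means by simulation:

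| Assumed SD (days) | Mean with 10% lost | Mean with 20% lost | Spurious difference |
|---|---|---|---|
| 60 | 249.2 | 239.8 | 9.4 |
| 100 | 239.6 | 223.9 | 15.7 |
| 140 | 229.3 | 207.5 | 21.9 |

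(Differences were taken before rounding.) Loss of 10% and 20% in equal groups is 12.65 + 25.3 = 37.95 subjects, so it agrees with the 38 reported. With 15% lost in both groups the spurious difference is zero, although both means are too low.

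**The case against.** The strongest case on the other side has four parts.

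- **Two links are inferred.** The Protocol does not say when randomisation took place, and it defines neither completion nor total treatment time. Having initial and final data could also describe exclusion for missing records. This is fair, and the links should be read as inferences. But enrolled and started are both 253 in a study that says it randomised its subjects, and follow-up ran for the length of treatment. The natural reading is that allocation came first and that completion ends the clock. Exclusion for missing final records would still be selection after allocation.
- **Aligner number may follow clinical indication.** The eligibility criteria refer to the aligner sets for which a subject is indicated, so randomisation may bear only on wear time. The document leaves this unresolved. Dropping the 38 would weaken a wear-time comparison just as much, and the 7- versus 12-aligner contrast is the one the Protocol says was made.
- **The bounds are not estimates.** This stands. Beyond the 15.0%, every figure rests on assumed inputs, and the actual bias may be near zero.
- **Details belong in an analysis plan, and the counts are already disclosed.** The absence of sensitivity analyses here is not itself an error, and the choice among methods is partly a matter of judgement. But the document does fix who was analysed, and disclosing 253, 215 and 38 does not tell the reader how the 38 fall across cohorts.

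**Conclusion.** The concern holds. The Protocol itself fixes a completers-only analysis for a study it describes as randomised, and leaves out 38 of 253 subjects (15.0%). That share follows directly from its counts. The selection can bias the comparison of both primary outcomes; whether it did, in which direction and by how much cannot be determined from the document.

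The 30.0-point band assumes equal pooled groups and a yes/no refinement outcome, and is a limit on what the data exclude rather than a likely error. The shifts of about 9 to 22 days describe one adverse scenario under an assumed distribution. The conclusion also rests on the natural reading that allocation preceded completion and that completion ends treatment time. It should be fixed, because the improvement is cheap and the present result cannot separate a cohort effect from an effect of who was left out.

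**What to change.** 1. Add an analysis of all 253 subjects in their assigned cohorts, labelled as added after the completer analysis, and base the randomised comparison on it. Keep the 215-completer result as a sensitivity analysis.
2. Analyse treatment time as time to completion, with non-completers censored at last contact. Because this assumes non-informative drop-out, add a sensitivity analysis that treats discontinuation as a competing or informative event.
3. For the refinement rate, use each cohort as allocated as the denominator, count any refinement ordered before discontinuation, and give best- and worst-case bounds for the remaining non-completers.
4. Report the 38 by cohort and reason.
5. If last-contact or refinement data for the 38 are not held, report the bounds and the cohort breakdown, and describe the existing result plainly as a completer analysis.

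The cost is some re-analysis and possibly wider intervals. The added analysis is post hoc and limited to whatever data exist for the 38, which the document does not describe. Time to completion also summarises treatment time differently from a mean in days, so the two should be presented side by side.
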